Statistical And Analytic Plan	
For the primary analysis of the fidelity outcome, linear mixed-effects models (LMM) will be used to compare the level of fidelity between the two implementation approaches (standard vs. virtual facilitation). We will report point estimates for the group mean difference along with a 95% confidence interval.
 
Generalized linear mixed models (GLMM) will be used for analysis of the secondary outcome of effectiveness.

DATA AND SAFETY MONITORING PLAN	
The study PIs will review interview and survey data as well as fidelity data on a quarterly basis for safety issues. In addition, the entire study team will meet monthly to discuss the study's progression and any potential safety or data concerns.

BACKGROUND AND RATIONALE

Major health crises like the COVID-19 pandemic have disproportionately impacted rural communities, which are frequently health professional shortage areas that lack health care infrastructure, including hospitals¹⁻³. As one of the most accessible health professionals in rural areas^{4,5}, community pharmacists are a notable exception to this lack of infrastructure. There are ≈68,000 community pharmacies in the U.S, many of which have convenient hours and offer free walk-in services⁶.

When compared to urban populations, individuals living in rural areas are more vaccine hesitant^{8,9} and have a higher prevalence of health conditions that increase their risk for severe COVID-19 illness and death¹². Higher vaccine hesitancy is strongly correlated with lower vaccination rates¹³, with rural counties driving lower state-level vaccination rates in the South^{14,15}, which has some of the lowest vaccination rates in the country. Unless vaccine hesitancy is addressed, low vaccination rates and a lack of vaccine mandates mean these communities remain susceptible to SARS-CoV-2 variants. Pharmacists, one of the most trusted sources of medication information¹⁶, can serve as strong allies to address vaccine hesitancy. Rural patients see their community pharmacist ~14 times per year; nearly three times more than they see a primary care provider¹⁷. Thus, pharmacists can address vaccine concerns on a monthly basis and make repeated vaccination offers.

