4.2 Secondary Outcome

The secondary outcome of effectiveness will be assessed on a monthly basis. Pharmacists will be instructed to deliver vaccine hesitancy counseling to one to two vaccine-hesitant individuals each week (towards a target of at least 5 per month). Using Qualtrics or a paper survey, pharmacists will document the following on a daily basis: A) how many vaccine-hesitant individuals they provided vaccine hesitancy counseling to; B) of those individuals, how many received a COVID-19 vaccine; C) the self-reported age, race, and gender of the individual who was counseled.

Effectiveness will be calculated as the proportion of counseled individuals who received a vaccine, or B/A. Individuals who are counseled and schedule a vaccine at a later date will not be counted in the numerator (B) until they have actually received a vaccine. Effectiveness scores will range from 0 to 1, with higher scores reflecting a greater percentage of vaccine-hesitant individuals who received a vaccine. During virtual facilitation, trial facilitators will be provided with bi-weekly effectiveness data so they can share the results with the pharmacies to assess performance and identify ways to improve implementation processes and intervention effectiveness.

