5.2 Secondary Outcome

For the secondary outcome of effectiveness, we will use generalized linear mixed models (GLMM) to investigate whether pharmacies are more effective at addressing vaccine hesitancy during virtual facilitation when compared to standard implementation. The effectiveness outcome will be binary (vaccine-hesitant patient accepts vaccine after counseling = 1; vaccine-hesitant patient does not accept vaccine after counseling = 0). We will report the odds ratio estimate of accepting the vaccine after counseling for the virtual facilitation approach (facilitation versus standard) along with a 95%

confidence interval. The model-building approach for our secondary effectiveness outcome will follow four analysis steps: 1) an unadjusted before/after of the effect of the virtual facilitation approach (ignoring period/time effect); 2) the inclusion of time period (i.e., steps) to examine if any potential intervention effect relates only to the intervention or also to an independent effect of calendar time; 3) an adjustment for patient's age, race, and gender and potential pharmacy-level confounders, such as pharmacy size; 4) the possible interaction between time period and intervention. The impact of virtual facilitation on effectiveness could potentially change over time if vaccine acceptance rates increase with time and as pharmacists gain experience with counseling vaccine-hesitant patients. We aim to explore this question through the inclusion of an interaction between period/time and intervention effect in Model 4. Additionally, the intraclass correlation coefficients (ICC) will be estimated and reported, so this information will be available for power analyses for future investigations using similar designs and outcomes. In order to reduce potential bias, during the virtual facilitation period, pharmacists will be instructed to approach patients that they did not approach during the standard facilitation period, which is feasible given the large number of unvaccinated individuals in the communities in which RURAL-CP pharmacies are located.

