Recommend the vaccine	
 Share your personal experience with the vaccine and that you trust it before you recommend it. This can help build their trust in the vaccine. After sharing your personal experience, then recommend the vaccine. "I wouldn't recommend the vaccine if I didn't think it was safe. I received it and I trust it. That's why I recommend that you get the vaccine - because I care about you and want you to keep you safe." You can also tie your recommendation to any factors that may put them or their family members at higher risk for severe COVID complications. If they are still unsure or refuse, then move to Step 5.
Try again later if they refuse or are unsure	
 As we've seen throughout the pandemic, many people who say they will never get the vaccine have since been vaccinated. So don't be discouraged if they refuse. React in a positive way and let them know you'll check in with them again. "Thanks for considering it. I'll check in with you again if I hear any new information about your concern." Since people can and do change their minds, it's important to try again during one of their next visits to the pharmacy. For regular customers, keep a list of people to follow up with or make a note in the pharmacy record to follow up.

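### Re-approach across the crossover is not reconciled, and the log as described cannot separate repeat contacts or credit a late vaccination to a condition, so the secondary effectiveness comparison can be misattributed

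*Combined protocol and SAP*

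**What the plan says.** **Who is approached.** Section 5.2, as a stated step against bias, says that in the facilitation period "pharmacists will be instructed to approach patients that they did not approach during the standard facilitation period". I read the period named there as standard implementation. Table 2 in the Appendix, under the last ASORT step, says of people who refuse or are unsure that it is "important to try again during one of their next visits to the pharmacy", and that for regular customers staff should "keep a list of people to follow up with or make a note in the pharmacy record to follow up". The Background and Rationale builds on the same idea: "pharmacists can address vaccine concerns on a monthly basis and make repeated vaccination offers".

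**What is logged.** Section 4.2 lists "A) how many vaccine-hesitant individuals they provided vaccine hesitancy counseling to; B) of those individuals, how many received a COVID-19 vaccine", and "C) the self-reported age, race, and gender of the individual who was counseled". Section 3.2 says that pharmacies provide no identifiable customer-level data, and section 8.2 says that effectiveness data are recorded in aggregate.

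**When a vaccination counts.** Under section 4.2, people who schedule a later vaccination "will not be counted in the numerator (B) until they have actually received a vaccine". No time window is given, and no rule says which period or condition receives the credit.

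**What the endpoint is.** Section 3.2 records how many customers *agreed*, section 4.2 how many *received* a vaccine, and section 5.2 models whether the patient *accepts*.

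**The concern.** Every pharmacy crosses from standard implementation to facilitation, so people counselled before the crossover remain customers after it. Two things can then happen. A person counselled under the standard condition may be vaccinated after the crossover and be logged in the facilitation period. Or a person who refused earlier may be counselled again and enter the facilitation denominator, and perhaps the numerator, as if new.

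The described log would show neither event. Adherence to the section 5.2 safeguard could not be checked, and the patient-level binary GLMM would treat two entries for one person as two people. At stake is the odds ratio for effectiveness, the trial's secondary outcome. Anonymous counts do not allow the missing information to be recovered later.

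**Working it through.** **Step 1. Inputs.** Figure 1 gives 6 blocks of 5 pharmacies, with 8 standard and 8 facilitation block-periods. Section 5.3 gives 10 patients per pharmacy per period, 5% versus 15% acceptance, and ICC 0.05. The plan's sample size reproduces: 16 block-periods × 5 × 10 = 800 patients, 400 per condition.

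**Step 2. Where the instructions collide.** Trying again within one condition is compatible with section 5.2. The conflict is confined to people who refused or were unsure in a standard period and return during facilitation. Table 2 says try again; section 5.2 says approach others.

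**Step 3. Late vaccination.** The documents give no rate of delay, so let s be the share of vaccinations logged in the pharmacy's next period (assumption, 10-40%). Each cell then shows

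observed rate = own rate × (1 − s) + previous cell's rate × s,

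with nothing carried into a pharmacy's first period. I fitted the standard and facilitation cells of Figure 1 by generalised least squares on the proportion scale, with a pharmacy random intercept, without period terms (as in Model 1 of section 5.2) and with them (as in Model 2). Estimated difference, in percentage points:

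| s | True 5% in both: Model 1 | True 5% in both: Model 2 | True 5% vs 15%: Model 1 | True 5% vs 15%: Model 2 |
|---|---|---|---|---|
| 0 | 0 | 0 | 10 | 10 |
| 10% | 0.4 | 0.0 | 9.6 | 8.8 |
| 20% | 0.8 | 0.0 | 9.2 | 7.6 |
| 40% | 1.6 | 0.0 | 8.4 | 5.2 |

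Hand check of Model 1 at s = 20%, using simple cell means. Six of the 8 standard cells are first periods and lose 20% of 5%, so the standard mean is 5 − 5 × 0.2 × 6/8 = 4.25%.
- With 5% in both conditions, the facilitation mean stays at 5%, a difference of 0.75.
- With 5% versus 15%, six of the 8 facilitation cells follow a standard cell, so the facilitation mean is 15 − 10 × 0.2 × 6/8 = 13.5%, a difference of 9.25.

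Both agree with the table up to the weighting.

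Model 2 shows no false gain under equal rates because all first periods of a cohort fall in the same calendar period, so the period term absorbs the loss. At 5% versus 15% it is diluted more than Model 1, because it leans on same-period contrasts. In December-January of the first season, for example, blocks 1 and 3 are in their first facilitation period while block 2 is still in standard. That contrast is (15 − 10s) − 5 = 8 points at s = 20%.

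**Step 4. Repeat contacts.** Let a share r of people counselled in facilitation be earlier refusers who accept at rate p (both assumed). The facilitation rate becomes (1 − r) × 15% + r × p, against a planned odds ratio of (0.15/0.85)/(0.05/0.95) = 3.35.
- With r = 10-30% and p = 0-5%, the rate is 10.5-14% and the odds ratio reads 2.23-3.09.
- With r = 10-30% and p = 25%, the rate is 16-18% and the odds ratio reads 3.62-4.17.

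**Step 5. Endpoint wording.** The delay problem arises under *received*. Under *agreed* or *accepts* it largely disappears, but repeat contacts remain.

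**The case against.** The strongest reply is that the plan has already dealt with this. Section 5.2 restricts facilitation to new people precisely to reduce bias, and Table 2 offers selected recommendations and sample wording, so a study-specific rule could be taken to prevail. Section 4.2 defines B as a subset of A, which suggests that credit follows the person counselled; the clause on late vaccination says when a person becomes a success, not where. Entries are daily, so pharmacy and date identify the condition at each contact. The log form is not in the documents and may hold more than section 4.2 lists.

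Much of this stands. Misattribution is possible, not prescribed, and the conflict is narrow. But nothing described carries the link between counselling and a later vaccination across the crossover. The date of a contact does not show whether it is the first. The pharmacy's own follow-up list is not described as study data.

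Two stronger readings are tempting. One is that the error favours facilitation. In Step 3 that holds only for the unadjusted model under equal rates; at the planned rates both models move against facilitation.

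The other starts from "Rural patients see their community pharmacist ~14 times per year". The mean gap is 52/14 = 3.7 weeks, and a reader might infer that 41% (exponential gaps) to 46% (regular visits, 3.71/8) of vaccinations carry over. That is the share of people whose next visit falls after an 8-week period, not a rate of delayed vaccination. Moreover, 2 of the 8 standard block-periods lead into another standard period, which leaves 6/8 of it, about 31-35%, crossing into facilitation. It does not support any value of s.

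**Conclusion.** The point holds as a gap in the plan. Three things are missing: a statement of how step 5 works across the crossover, a way to recognise repeat contacts, and a rule that credits a late vaccination to a condition.

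The size is unknown. The ranges in the working rest on assumed values of s, r and p and on a linear approximation to the planned GLMM, and the direction is not fixed. A reader might infer that the comparison is certainly wrong or that facilitation is certainly flattered; the documents support neither. The primary fidelity outcome is untouched, because it is rated on standardized patients. This is a cheap improvement to the secondary outcome.

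**What to change.** - Reconcile the section 5.2 instruction with Table 2 step 5, stating what applies to people who refused or were unsure before the crossover.
- Add two non-identifying fields to each log entry: first or repeat counselling of this person, and the condition in force at first counselling. This is compatible with sections 3.2 and 8.2.
- Settle on one endpoint wording across sections 3.2, 4.2 and 5.2.
- In sections 4.2 and 5.2, count each person once, in the condition of first counselling, with vaccination within one fixed window of the same length in both conditions. Analyse repeat contacts separately.

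The cost is two tick-boxes, some wording, slightly fewer rows in the main analysis, and a short wait for the window to close after the last period. If collection has already begun, the crediting rule can still be fixed before analysis. The limitation should then be stated, with a sensitivity analysis where the data allow.

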5.3 Power Analyses

For the primary outcome of fidelity, captured at the pharmacy level, we wish to compare the fidelity scores under standard implementation versus fidelity scores under virtual facilitation. We expect each pharmacy to have approximately 4 fidelity assessments per time period (i.e., a period of 8 weeks). A sample of 30 pharmacies in an incomplete stepped-wedge cluster-randomized design with six periods (five steps), and an average of 10 fidelity assessments per pharmacy yields a total sample size of 320 assessments, which achieves over 90% power to detect a difference between means of 0.53 with a standard deviation of 1 (i.e., moderate effect size). The test statistic is based on a two-sided Wald Z-test with $ICC = 0.6$ and $\alpha = 0.05$. Given that we will have repeated fidelity measures from the same pharmacists over time, we have specified a conservative ICC (which in a stepped wedge design does not impact power calculations significantly).

For the secondary outcome of effectiveness, we expect each pharmacy to identify approximately 10 vaccine-hesitant patients during each time period (i.e., a period of 8 weeks). A sample of 30 pharmacies in an incomplete stepped-wedge cluster-randomized design with six periods (five steps) and an average of 27 patients per pharmacy yields a total sample size of 800 patients, which achieves over 90% power to detect a difference between effectiveness proportions of 10%. The proportion of vaccine-hesitant patients accepting the vaccine during the virtual facilitation approach is assumed to be 15% compared to 5% under the standard implementation period. These estimates are based on a review of reported changes in vaccine acceptance for evidence-based vaccine hesitancy interventions⁴⁰. The test statistic is based on a two-sided Wald Z-test with $ICC = 0.05$ and $\alpha = 0.05$. We note that the actual sample size should exceed 800 patients since we expect pharmacies will continue to identify vaccine-hesitant individuals during the follow-up periods.

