4.3 Other Measures

Acceptability, appropriateness, and feasibility of the vaccine hesitancy intervention and implementation approaches (standard, facilitation) will be measured using validated surveys³³. Each

measure includes 4 items (e.g., “intervention X seems doable” [feasibility]) measured on a 5-point response scale that ranges from “strongly disagree” (coded as 1) to “strongly agree” (coded as 5). For each pharmacy, we will average scores across the pharmacy staff members who complete the surveys.

Uptake will be calculated as the number of times vaccine hesitancy counseling was offered divided by the number of individuals who expressed vaccine hesitancy when offered the vaccine.

Sustainment will be assessed by the continued measurement of fidelity, effectiveness, and uptake during the “follow-up” periods.

*Organizational structure and context measures*³⁴: one pharmacist per pharmacy will complete the Organizational Structure survey^{35,36}, which measures: location, type (e.g., independent, chain), setting (e.g., retail, specialty), size (weekly prescriptions, staffing), technological capacity (dispensing system), and services provided. The Organizational Context measure (completed by 5 pharmacy staff members) assesses CFIR inner setting constructs³⁴ that reflect organizational culture/capacity for change³⁷, learning climate, leadership, and resources^{38,39}. All items are measured on a 5-point agree-disagree response scale, with higher scores reflecting a stronger implementation context. For each pharmacy, we will average scores across the five pharmacy staff members who complete the surveys.

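### The over-90% power claimed for the vaccination outcome is not reached by the period-adjusted GLMM: with calendar period as categories and a variance reflecting both assumed rates, 800 patients give roughly 65-80%

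*Combined protocol and SAP*

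**What the plan says.** Section 5.3 expects about 10 vaccine-hesitant patients per pharmacy per 8-week period. It states that "an average of 27 patients per pharmacy yields a total sample size of 800 patients, which achieves over 90% power" to detect a 10-point difference. Acceptance "during the virtual facilitation approach is assumed to be 15% compared to 5% under the standard implementation period". "The test statistic is based on a two-sided Wald Z-test with" ICC 0.05 and alpha 0.05. The section adds that "the actual sample size should exceed 800 patients since we expect pharmacies will continue to identify vaccine-hesitant individuals during the follow-up periods", so the 800 itself excludes follow-up.

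Section 5.2 gives the analysis: "we will use generalized linear mixed models (GLMM) to investigate whether pharmacies are more effective at addressing vaccine hesitancy during virtual facilitation", reported as an odds ratio with a 95% confidence interval. Four model steps follow. Step 1 is an unadjusted before/after comparison without a period term. Step 2 is "the inclusion of time period (i.e., steps) to examine if any potential intervention effect relates only to the intervention" or also to calendar time. Steps 3 and 4 add covariates and a period-by-intervention interaction. Section 5.2 does not name a decisive step or say how period enters the model, and Section 5.3 does not tie its power figure to any step.

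**The concern.** In a stepped wedge, facilitation always comes after standard implementation within a pharmacy. A model without period therefore mixes the effect of facilitation with any change in acceptance over time. The plan itself expects that such change is possible: "The impact of virtual facilitation on effectiveness could potentially change over time if vaccine acceptance rates increase with time". Step 2 is where the two are separated, so its power is what matters for H2.

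Period adjustment is expensive in this layout because most periods contain only one condition. The outcome variance matters too. A proportion of 15% has variance 0.1275, against 0.0475 at 5%, and using the smaller value in both arms understates the standard error. If the quoted power rests on either shortcut, the chance of missing a true 10-point effect is about 20-35% and not under 10%. That changes how a null result on H2 should be read.

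**Working it through.** **Inputs.** Figure 1: six blocks of 5 pharmacies; blocks 1 and 4 run S-F, blocks 2 and 5 run S-S-F, blocks 3 and 6 run S-F-F (S = standard, F = facilitation; follow-up left out). Section 5.3: 10 patients per pharmacy-period, 5% versus 15%, ICC 0.05, two-sided alpha 0.05.

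**Sample size.** Block-periods: 2 + 3 + 3 + 2 + 3 + 3 = 16. Then 16 × 5 = 80 pharmacy-periods, and 80 × 10 = 800, or 800/30 = 26.7 per pharmacy. This matches the plan.

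**Layout.** Standard/facilitation pharmacies by period: 15/0, 5/10, 0/10, 15/0, 5/10, 0/10. Only the second period (Dec-Jan of the first season) and the fifth (Oct-Nov 2024) contain both conditions.

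**Method.** Generalised least squares (GLS) on pharmacy-period means with a random pharmacy intercept. With total variance σ², the between-pharmacy variance is 0.05σ² and the residual variance of a cell mean is 0.95σ²/10. Power = Φ(0.10/SE − 1.96).

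**Variance options.**
- 5% rate in both arms: 0.05 × 0.95 = 0.0475
- Average of the two arms: (0.0475 + 0.1275)/2 = 0.0875
- Pooled 10% rate: 0.10 × 0.90 = 0.09
- Arm-specific: 0.0475 and 0.1275

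**Reproducing the plan's figure.** With six period categories and 0.0475 in every cell, SE = 0.0294. Then 0.10/0.0294 − 1.96 = 1.44, and power is 92.5%. So the stated figure can be obtained.

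**Changing only the variance, still six categories.** With a common variance, the SE scales with its square root.
- Average: 0.0294 × √(0.0875/0.0475) = 0.0399; 0.10/0.0399 − 1.96 = 0.55; power 70.7%
- Pooled: 0.0294 × √(0.09/0.0475) = 0.0405; 0.10/0.0405 − 1.96 = 0.51; power 69.5%
- Arm-specific: SE 0.0359-0.0377, depending on how the ICC is placed; power 75.5-79.5%

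**Changing the period coding, variance reflecting both rates.** The GLMM column is the Wald test in a simulated random-intercept logistic model with marginal rates of 5% and 15% and no true period effect. Its two values use a pharmacy SD of 0.75 on the logit scale (ICC about 0.05 on the proportion scale) and 0.416 (ICC 0.05 on the latent scale).

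| Period term | GLS power | GLMM power |
|---|---|---|
| Six categories | 69.5-79.5% | 65.3%, 71.7% |
| Season + three within-season step categories | same as six categories | 67.3%, 70.9% |
| Season + within-season trend | 72.6-79.8% | 78.0%, 81.7% |
| One linear trend over all six periods | 98.0-98.9% | 98.0%, 99.3% |
| No period term | 99.6% or more | 99.9%, 99.5% |

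The simulations used 8,000 runs per value for six categories and for season plus trend, 6,000 for season plus step categories, and 1,500 for the last two rows. Type I error with six categories and 10% in both arms was 4.9% (2,000 runs).

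**Sensitivity, six categories, GLS.** ICC from 0 to 0.2 gives 68-85%. A cluster autocorrelation of 0.8 gives 67-74%.

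**Check on the primary outcome.** The same method with 4 assessments per period (80 × 4 = 320), SD 1, ICC 0.6 and six categories gives SE 0.1522. Then 0.53/0.1522 − 1.96 = 1.52, and power is 93.6%, in line with the primary statement. This suggests, but does not prove, that the secondary figure came from categorical period with the 5% variance throughout.

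**The case against.** The strongest reply is that the figure is not wrong. It can be reproduced, the step 1 model without period is a planned analysis with power above 99%, and Section 5.2 never says that period is categorical. This stands as far as it goes: the arithmetic is sound under some choices, and the fault is that those choices are not stated. It does not rescue the claim. Step 1 is by its own description an unadjusted comparison. A single straight line across two vaccine seasons separated by a gap is hard to defend as a term for steps. The more flexible season-plus-trend coding is still below 90%.

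A second reply is that follow-up patients will add information. If the 20 follow-up pharmacy-periods are added to the six-category model, power is about 88-90% with one common follow-up effect, and 92-94% if they count as facilitation. These figures need patients outside the stated 800 and an assumption that the plan does not make. With separate effects for immediate and delayed follow-up, power returns to about 70-78%. Counting follow-up as facilitation also sits badly with Section 2.1, where facilitation has by then ended, and with Section 4.3: "Sustainment will be assessed by the continued measurement of fidelity, effectiveness, and uptake during the" follow-up periods.

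Third, this is a secondary outcome, and its confidence interval will show any imprecision. That limits the weight of the point, but H2 is a stated hypothesis with its own power claim.

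**Conclusion.** The concern holds. For 800 patients at ICC 0.05, with follow-up excluded, a period-adjusted analysis with period as categories and a variance consistent with the plan's own 5% and 15% has roughly 65-80% power: 69.5-79.5% by GLS and 65-72% for the simulated GLMM Wald test. The shortfall comes from period adjustment and the both-rate variance together. Either one alone leaves power above 90%: 92.5% with categories and the 5% variance, and 99.6% or more by GLS with no period term and a both-rate variance.

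The result assumes exactly 10 patients per pharmacy-period, a constant pharmacy effect over time and, in the simulations, no true period effect. The exact figure depends on the variance approximation and ICC scale. The conclusion that it is below 90% did not, for any ICC from 0 to 0.2 that was tried. It should be fixed, but it does not threaten the design or the primary analysis.

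**What to change.** In Section 5.3, name the model, the period coding and the variance behind the secondary power figure, and restate the power for the step 2 GLMM. Suggested wording:

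> With the step 2 model of Section 5.2 (random-intercept logistic GLMM, calendar period as categories, ICC 0.05, 5% versus 15%, two-sided Wald test), 800 patients give roughly 65-80% power depending on the variance approximation (about 65-72% for the GLMM Wald test). Follow-up patients, seen after facilitation has stopped, are not counted as facilitation in this figure.

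The trial statistician should confirm the figure with the model actually intended. If another period coding is meant, name it and give its power. No separate power figure for follow-up is needed.

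The cost is wording in one section and a less favourable secondary power figure. The sample size, the design and the primary power statement do not change.
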